## 4. REGISTRATION PROCEDURES

### 4.1 Patient Registration

Each subject enrolled in the study is to be registered into the UWCCC OnCore Database prior to starting protocol treatment. Research personnel at WON sites who enter data into OnCore must have completed human subjects training and Health Insurance Portability and Accountability Act (HIPAA) training. WON site research personnel receive training from UWCCC staff on how to enter subject data into OnCore.

At the time of registration, the following will be required and verified by UWCCC:

- Copy of required laboratory tests
- Signed subject consent form
- HIPAA authorization form
- *Eligibility Screening Worksheet*

To complete the registration process, UWCCC staff will:

- assign a subject study number
- register the subject on the study
- fax or e-mail the subject study number to the participating site

## **4.2 General Guidelines**

Following registration, subject must have cycle 1 day 1 within 7 days. Issues that would cause treatment delays should be discussed with the Principal Investigator. If a subject does not receive protocol therapy or MR diet following registration, the subject may be replaced.

## **5. TREATMENT PLAN**

### **5.1 Overview of treatment plan**

This is a phase 2 trial in which subjects will receive ONC201 with a MR diet.

### **5.2 ONC201 administration**

The study drug, ONC201, will be supplied in capsule form for oral dosing. ONC201 625 mg (5 tablets of 125 mg each) will be given by mouth on Days 3 and 4 of each week for each cycle (administered on days 3,4, 10,11 and 17,18). Treatment will be administered primarily on an outpatient basis, but can be administered as an inpatient. A cycle is equal to 21 days.

Subjects should take the dose of ONC201 specified by their physician 2 hours prior or 2 hours following food or a meal. If the subject vomits after taking ONC201, they should not retake the dose. Missed doses will not be made up, if more than 1 day pass from the intended day of administration.

ONC201 should be taken with a glass of water and consumed over as short a time as possible. Subjects should swallow the capsules as a whole and not chew them. Do not crush or empty the capsule. If vomiting occurs during the course of treatment, no re-dosing of the subject is allowed before the next scheduled dose. The occurrence and frequency of any vomiting during a treatment cycle must be noted as an adverse event.

### **5.3 Methionine-restricted diet**

Under the supervision of a registered dietitian (either at the site or from the coordinating site) and the site investigator, subjects will receive an individualized dietary prescription that incorporates a methionine-free amino acid-modified

medical food (Hominex-2, Abbott Nutrition) supplemented with low-methionine foods (**Table 2**). Hominex-2 contains a mixture of L-amino acids but lacks methionine. Subjects will be instructed by the dietitian in the preparation of Hominex-2 shakes to deliver 100% of daily protein requirements (0.8 g/kg/day) and 75% of the caloric requirements. The remaining calories will be met with low-methionine foods, including fruits, vegetables, grains (*e.g.*, specified cereal and bread), margarine and cooking oils. Subjects will be provided with a list of foods that are low in methionine. Calories will not be restricted. Subjects will be encouraged to follow their usual level of physical activity and instructed to maintain a daily diet and exercise diary that will be reviewed by the dietitian. Subjects will take the MR diet days 1 through 5 of each week (defined as a 7-day period) while taking the ONC201. Subjects may resume a general diet on days 6 and 7 each week. Phase I and phase II trials of a methionine-free diet alone or in combination with chemotherapy in subjects with metastatic or recurrent solid tumors have confirmed the safety and tolerability of methionine deprivation (up to 39 weeks)[24, 25].

A 24-hour dietary recall exercise [40] will be completed by a dietitian prior to starting the methionine restricted diet during cycle 1. The recall and food diaries will be analyzed using Food Processor® Nutrition and Fitness Software, ESHA Research, Salem, OR, USA. Food intake will be entered in and a report detailing the nutritional components of the food taken will be generated and provided back to the dietitian. Gender, age, height and weight will be entered for use with the analysis of the diet taken. This dietary analysis will not be provided to the subjects.

**Table 2: Methionine-restricted diet shakes**

Regimen Description					
Agent	Premedications; Precautions	Dose	Route	Schedule	Cycle Length
Methionine-free amino acid- modified medical food	None	shakes	Oral	Per dietitian recommendation	Days 1 through 5* of every 7- day period. Cycle = 21 days

\*Subjects should follow the methionine restricted diet for days 1-5 of every 7-day period. However, 1 day of methionine restriction may be skipped in this 5-day restriction period if needed to allow flexibility around holidays, vacations, etc. The 4-5 days of the diet during each 7-day period must be consecutive. The diet must be

followed for a minimum of 24 hours prior to the collection of CTCs and for a minimum of 24 hours prior to dosing with ONC201.

The subject will be requested to maintain a medication diary of each dose of medication. The medication diary (one for ONC201 and for the shakes) and the diet/exercise diary will be returned to clinic staff at the end of each cycle of therapy. It will not be a deviation if the subject isn't able to complete the diet/exercise diary. Subjects will meet with the dietitian on day 1 of cycles 1 and 2 to review the diet/exercise diary. Additionally, the dietitian will contact the subject during the initial week of cycle 1 to assess tolerance of the diet and to address questions the subjects may have. Subjects will be able to contact the dietitian during normal business hours to discuss dietary questions or concerns related to the study.

Recipes for the methionine restricted shakes will be developed to fit the needs of individual subjects (taste preferences, energy needs, etc.).

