### **2.2 Secondary Objectives:**

2.2.1 To determine progression-free survival (PFS) to ONC201 with a methionine-restricted diet in patients with metastatic TNBC.

2.2.2 To determine clinical benefit rate (complete and partial response plus stable disease) (CBR) at 4 months to ONC201 with a methionine-restricted diet in patients with metastatic TNBC.

2.2.3 To determine overall survival (OS) to ONC201 with a methionine-restricted diet in patients with metastatic TNBC.

2.2.4 To determine the safety of adding a methionine-restricted diet to ONC201 in patients with metastatic TNBC

2.2.4 To assess metabolic indices in patients with metastatic TNBC treated with ONC201 and a methionine-restricted diet.

2.2.5 To assess the expression of TRAIL receptor in CTCs prior, during and upon progression in patients with metastatic TNBC treated with ONC201 with a methionine-restricted diet.

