- (2) Blood will be taken to assess plasma methionine levels at baseline, cycle 2 day 5, then day 5 of every other cycle, and at end of treatment. Subjects must be fasting. If necessary, these labs may be drawn as early as day 2, but prefer to be as close to day 5 as possible without going over.
- (3) If clinically indicated.
- (4) Optional biopsy prior to study entry.
- (5) Blood for circulating tumor cells will be taken at baseline, day 5 of cycle 2, and at end of treatment. If necessary, these labs may be drawn as early as day 2, but prefer to be as close to day 5 as possible without going over.
- (6) For women of childbearing potential. To be completed within 7 days of randomization. Must be repeated at cycle 1 day 1 if not completed in previous 7 days.
- (7) Subjects whose treatment is interrupted or permanently discontinued due to an adverse event (including lab values) should be followed per section 11.1.1.
- (8) Waist circumference, optional if not possible due to site limitations. Not required at screening.
- (9) CMP to include sodium, potassium, chloride, carbon dioxide, glucose, BUN, creatinine, calcium, albumin, total protein, alkaline phosphatase, aspartate aminotransferase (AST), alanine aminotransferase (ALT), and total bilirubin.
- (10) CT chest with or without contrast and CT with contrast or MRI of Abdomen/Pelvis to be completed during screening and  $\leq$  7 days prior to every third cycle starting at cycle four (approximately every 9 weeks; e.g. cycles 4, 7, 10, etc.). If subjects discontinue study treatment prior to disease progression, scans during follow-up will be completed per standard of care, but RECIST measurements must be completed until disease progression or start of new anti-cancer therapy.
- (11) Homocysteine/cysteine level at: baseline and every 3 cycles while on study (C1, C4, C7, etc.) and at end of treatment.
- (12) One block or 10 unstained slides.
- (13) labs/physical exam/ECOG PS does not need to be repeated if done within 7 days prior to C1D1

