### **8.2 Circulating tumor cells (CTCs)**

If funding is secured, CTCs will be enumerated and evaluated for TRAIL expression. We hypothesize that treatment with MR diet will increase the expression of TRAIL receptors on CTCs and reduce the number of CTCs.

**Time points:** CTCs will be collected at baseline, on day 5 of cycle 2, and at end of treatment. If the CTC sample is not collected at baseline, the remaining samples should not be collected. Missed CTC samples will not be considered a protocol deviation.

Please note that CTC samples must be shipped Monday –Thursdays only. Samples must be shipped to arrive at the [name] lab by Fridays by 12:00 p.m. CTC samples will be drawn only at those sites identified by the coordinating site as having adequate resources (shipping and funding) to provide the samples.

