### **8.3 Plasma methionine and methionine metabolites**

Blood will be collected after an overnight fast before dietary methionine restriction at baseline, cycle 2 day 5, then day 5 of every other cycle, and at end of treatment. Plasma will be stored at -80° C for analyses of methionine and its metabolites. Plasma concentrations of methionine and methionine metabolites [5'-methylthioadenosine (MTA), homocysteine (Hcy), S-adenosylhomocysteine (SAH), and S-adenosylmethionine (SAM)] will be determined by high-throughput targeted LC-MS assay to measure methionine and these metabolites. Using these methods, we demonstrated that TNBC cells grown in 0% methionine have robust reductions in methionine levels and modest reductions in some methionine metabolites. Plasma methionine levels are predicted to serve as an index of dietary compliance.

Blood samples (one 6 mL heparinized green top tube per timepoint) will be drawn and processed at the CRU, stored in [name] lab at -80° C, and sent in batches to the Laboratory of [name] in the UW Department of Chemistry. All samples provided will be identified by UWCCC study number, unique subject number and date and time sample was collected. Outside sites should refer to the Study Procedures Manual for collection, processing, labeling, and shipping instructions.

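### The 24-hour diet rule in Table 2 does not exempt the baseline CTC draw, so read literally the reference sample for the TRAIL-receptor objective is taken on the diet

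*Combined protocol and SAP*

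**What the plan says.** - **Diet rule.** The Table 2 footnote in section 5.3 makes it mandatory that the diet be "followed for a minimum of 24 hours prior to the collection of CTCs". It sets the same 24-hour minimum before ONC201 dosing. No time point is named for the CTC part.
- **CTC time points.** Section 8.2: "CTCs will be collected at baseline, on day 5 of cycle 2, and at end of treatment". Calendar footnote 5 in section 7 agrees: "Blood for circulating tumor cells will be taken at baseline, day 5 of cycle 2, and at end of treatment". It then adds: "If necessary, these labs may be drawn as early as day 2, but prefer to be as close to day 5 as possible", without saying which draws this covers. The calendar has no CTC draw at screening; the baseline draw is in the Cycle 1 column, whose window is Day 1 plus or minus 2 days.
- **Treatment start.** Section 5.3: "Subjects will take the MR diet days 1 through 5 of each week". Section 5.2: ONC201 "will be given by mouth on Days 3 and 4 of each week for each cycle".
- **Objective.** Objective 2.2.5: "To assess the expression of TRAIL receptor in CTCs prior, during and upon progression". Section 8.2 hypothesizes that the diet itself will raise TRAIL-receptor expression on CTCs and lower their number.
- **How other baselines are worded.** For plasma methionine and its metabolites, section 8.3 states: "Blood will be collected after an overnight fast before dietary methionine restriction at baseline". Section 5.3 likewise puts the 24-hour dietary recall before the diet starts. Neither section 8.2 nor footnote 5 says this for CTCs, and footnote 1 does not say it for the metabolic indices (glucose, insulin, IGF-1, leptin).

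**The concern.** A site that follows the footnote as written cannot take a CTC baseline before the diet without breaking a mandatory rule. A site that reads baseline in its ordinary sense will draw before the first shake. Both kinds of sample would be pooled under one label.

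The CTC work asks whether the diet changes TRAIL-receptor expression and CTC number. If the reference sample already contains part of the diet effect, that part drops out of the comparison. The baseline also controls the rest of the series: under section 8.2, if it is not collected, the later CTC samples should not be collected either. With at most 34 subjects in the efficacy design, and CTCs drawn only at selected sites, a compromised reference could not be recovered afterwards.

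**Working it through.** The plan gives no figure to reproduce here. The check is day arithmetic on its own schedule.

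**Step 1: which days satisfy both the rule and the window?** The window ends on Day 1 + 2 = Day 3. With the diet starting on Day 1, nominal diet time at the start of day d is 24 × (d − 1) hours.

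| Baseline draw | Nominal hours on diet | Meets 24-hour rule | Before the diet |
|---|---|---|---|
| Before Day 1, in window | 0 | no | yes |
| Day 1 | 0 to 24 | no | only if before the first shake |
| Day 2 | 24 to 48 | yes | no |
| Day 3 (first ONC201 day) | 48 to 72 | yes | no |

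No row meets the rule and also precedes the diet.

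**Step 2: exposure before the comparator, cycle 2 day 5.**
- Diet days: cycle 1 has 3 weeks × 5 days = 15. Cycle 2 days 1 to 4 add 4. Total 15 + 4 = 19.
- If the one permitted skip is used each week: 3 × 4 = 12, plus 3 or 4 in the current week, gives 15 to 16.
- ONC201 doses: cycle 1 has 3 weeks × 2 = 6. Cycle 2 days 3 and 4 add 2. Total 6 + 2 = 8.

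**Step 3: how much of that exposure could a late baseline already hold?** A Day 3 baseline follows 2 completed diet days: 2/19, or about 11% of cumulative diet days. Counting the current week only, it is 2 of 4. Neither ratio is an estimate of bias, because the documents do not say how quickly CTC expression responds in patients.

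**Step 4: the early-draw allowance.** If the cycle 2 sample is taken on day 2, it follows 15 + 1 = 16 diet days and 6 doses, but only 1 diet day in that week, fewer than a Day 3 baseline (2).

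**Step 5: metabolic indices.** The 24-hour rule does not mention them. Their baseline is in the same Cycle 1 column and has no pre-diet wording, so the window alone would allow a draw after up to about 48 hours of diet at the start of Day 3.

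**The case against.** The best reply is that the footnote was never meant for the baseline. It sits with rules about which diet day may be skipped in a treatment week, and it fits the allowance to draw a day 5 sample as early as day 2. Applied to every draw, it would also require diet before the end-of-treatment sample, which is scheduled 35 days after the last dose (plus or minus 5). The plus or minus 2 days may move the start of the cycle, and the diet with it, rather than allow a draw on treatment Day 3. Section 8.2 also defers collection instructions to a Study Procedures Manual that is not part of these documents.

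Most of this stands as evidence of intent. A reader might infer that the trial plans to take its baseline on the diet; the documents do not show that. What remains is that no section exempts the baseline CTC draw or places it before the diet, although sections 5.3 and 8.3 do so for other baseline items. The 24-hour rule conflicts with a pre-diet baseline however the window is read.

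Three further inferences should be resisted:
- **That up to half the contrast is lost.** This counts only the current week. The cycle 2 day 5 sample also follows a full cycle of diet and 8 ONC201 doses, and section 1.5.2 describes ONC201 as itself acting on the TRAIL receptor DR5, so the contrast is not one of diet days alone.
- **That homocysteine has no pre-diet baseline.** Section 8.3 lists it among the metabolites in the sample drawn before the diet. The separate test in footnote 11 feeds grading on absolute levels (Tables 3 and 4), not change from baseline.
- **That the metabolic indices are equally exposed.** Only the window and the silence of footnote 1 bear on them. They share a fasting schedule with plasma methionine, so one pre-diet visit may serve both, and section 13.7.2 plans only frequency tables and descriptive statistics.

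**Conclusion.** The point holds as an unreconciled instruction that, followed literally, yields a wrong reference sample for objective 2.2.5. The likely direction is toward no change in TRAIL-receptor expression and CTC number between baseline and cycle 2 day 5. This assumes that the diet acts in the hypothesized direction and that some effect appears within the first one to two days. The size cannot be stated: it is nil if sites draw before the first shake, and it could be most of the effect if the response is complete within 48 hours.

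The severity is minor. CTC work depends on funding (section 1.6) and is done only at selected sites, and missed CTC samples are not deviations (section 8.2). The metabolic-index gap is a matter of consistency. The ORR endpoint and the two-stage decision rule are untouched.

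**What to change.** 1. **Table 2 footnote:** limit the CTC part of the 24-hour rule to the on-treatment draw at cycle 2 day 5.
2. **Section 8.2 and calendar footnote 5:** state that the baseline CTC sample is drawn before the first diet day and before the first ONC201 dose, and that the allowance to draw from day 2 applies only to day 5 draws.
3. **Calendar footnote 1:** for consistency, give the baseline metabolic indices the same pre-diet wording that section 8.3 uses.

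The Study Procedures Manual should be checked against the revised text. The cost is a wording amendment; no samples, visits or subjects are added.

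If baseline samples have already been drawn, record for each whether it came before or after the first shake, and report any on-diet baselines separately in the CTC analysis.

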#### **5.4 Study drug compliance and accountability**

Compliance will be assessed by the investigator and/or study personnel at each subject visit at each participating site. Drug diaries will be used by subjects to record study medication taken and number of shakes taken. A drug accountability log at each respective site will be used to track the receipt and dispensing of ONC201.

#### **5.5 Concomitant medications**

##### **5.5.1 Allowed concomitant medications**

Medications required to treat AEs, manage cancer symptoms, concurrent diseases and supportive care agents, such as pain medications, anti-emetics and anti-diarrheal medications are allowed. In general, the use of any concomitant medication deemed necessary for the care of the subject is permitted in this study, except as specifically prohibited below.

The subject must be told to notify their respective participating investigational site staff about any new medications she takes after the start of the study treatment. All medications (other than study drugs) and significant non-drug therapies (including vitamins, herbal medications, physical therapy and blood transfusions) administered within 30 days of study entry and during the study must be listed on the Concomitant medications/Significant non-drug therapies section of the subject record.

##### **Bisphosphonates and Denosumab:**

Bisphosphonates and denosumab are permitted for the treatment of osteoporosis and prevention of skeletal related events for subjects with bone metastases.

##### **Hematopoietic growth factors:**

Hematopoietic growth factors may be used according to ASCO guidelines.

### **5.5.2 Prohibited concomitant medications**

To date, no prohibited concomitant medications have been identified.

### **5.6 Supportive care Guidelines**

Supportive measures including analgesics, blood transfusions, anti-microbials and hematopoietic colony stimulating factors for treatment of cytopenias are permitted.

#### **Nausea/vomiting:**

Subjects with treatment-related nausea should be treated initially with a phenothiazine (prochlorperazine – 10 mg every 8 hours orally as needed). If this is inadequate, a benzodiazepine or ondansetron 4-8 mg orally should be added until acute nausea is controlled or toxicity is limiting.

After acute nausea has resolved, consideration should be given to initiation of prophylactic antiemetic therapy. If nausea recurs despite reasonable medical intervention (as outlined above), dose reduction will be needed as described.

#### **Diarrhea:**

Diarrhea should be managed with loperamide: 4 mg at first onset, then 2 mg every 2-4 hours until diarrhea is controlled (maximum = 16 mg loperamide per day).

#### **Neutropenia and Neutropenic fever and other cytopenias:**

Subjects with neutropenic fever or infection should be evaluated promptly and treated with IV antibiotic therapy or therapeutic colony-stimulating factors as appropriate following the ASCO guidelines. Packed red blood cell and platelet transfusion should be administered as clinically indicated.

## **6. TOXICITIES AND DOSE DELAYS/DOSE MODIFICATIONS**

The NCI Common Terminology Criteria for Adverse Events (CTCAE) version 5.0 (v5.0) will be used to grade adverse events.

Subjects enrolled in this study will be evaluated clinically and with standard laboratory tests before and at regular intervals during their participation in this study as specified in Study Calendar.

Subjects will be evaluated for adverse events (all grades), serious adverse events, and adverse events requiring study drug interruption or discontinuation as specified in Study Calendar.

### **6.1 Adjustments to Methionine-Restricted Diet**

The dietitian may modify the volume and concentration of shakes to increase tolerability.

Best supportive care should be used for side effects attributable to the methionine restricted diet/medical food.

Subjects who discontinue the methionine restricted diet may continue ONC201.

**Table 3: Dose adjustment rules for Adverse Events (in addition to Table 5 below)**

CTCAE Grade	Management for the methionine-restricted diet
Weight loss	
Grade 2 or higher	Methionine restricted diet must be discontinued.
Homocysteine levels (to be captured as: Metabolism and Nutrition disorders – other, specify)	
Grade 2 or higher	Methionine restricted diet must be discontinued

Normal homocysteine levels are 5-15 micro mol/L.

For purposes of this study homocysteine levels will be graded per the table below:

**Table 4:**

	Grade 1	Grade 2	Grade 3
Homocysteine Level	$\geq 15 - < 30$ micro mol/L	$\geq 30 - < 100$ micro mol/L	$\geq 100$ micro mol/L

